#### **1.2. Construction of Study Outcomes**

We use a combination of South Carolina vital records, Medicaid claims, and hospital discharge records to construct study outcomes. In cases where outcomes differ between records, (e.g. gestational age at delivery, birthweight) we will use estimates from South Carolina vital records.

##### **1.2.1 Primary Outcome**

Our primary outcome for this domain is an adverse birth outcome, which we define as having a preterm birth (less than 37 weeks' gestation), a newborn being small for gestational age (less than 10th percentile of US births conditional on gestational age), having low-birth weight (less than 2500 grams), or experiencing perinatal mortality (fetal death occurring at or after 20 weeks' gestation or mortality in the first 7 days of life). Data for the adverse birth outcome will come from South Carolina birth records, death records, and fetal death records.

For mothers with multiple births, we define the outcome based on having an adverse birth outcome for any child from the index pregnancy. While preterm birth and other adverse birth outcomes may be more common among multiple births, we anticipate that rates of multiple births will be equal across treatment and control arms. We may also explore alternative specifications of this outcome that include only singleton births.

### 1.2.1 Secondary Outcomes

We will examine several secondary infant and maternal outcomes. For infant outcomes, we will examine each adverse birth outcome individually (SGA, preterm, low birth weight, perinatal mortality). We will also examine large-for-gestational age ( $>90^{\text{th}}$  percentile of US births conditional on gestational age), very low birth weight ( $<1500\text{g}$ ), a continuous measure of birth weight, and extremely preterm ( $<28$  weeks gestation) using birth certificate records. We will also examine neonatal morbidity, defined as assisted ventilation immediately after delivery, assisted ventilation for more than six hours, seizure, receipt of surfactant replacement therapy, or receipt of antibiotics for suspected sepsis using data from the birth certificate.ii,10,11 Finally, we will examine NICU admission of at least overnight, defined as a claim with a procedure code of 99468, 99469, 99477, 99478, 99479, or 99480 on the day of delivery and also on the following day.

We will also examine several maternal health related secondary outcomes at birth, including cesarean delivery (from the birth certificate) and severe acute maternal morbidity from hospital discharge and Medicaid data (as defined by the Centers for Disease Control and Prevention). We will examine maternal mortality up to one year after birth using vital records. We will examine receipt of any postpartum visit within the first 12 weeks postpartum using Medicaid claims data, defined as a claim with a diagnosis code of Z39 or a HCPCS code of 59430.

Next, we will examine the outcome of neonatal abstinence disorder and/or maternal drug/substance abuse both during the index pregnancy period and over the period spanning the index pregnancy and the first 24 months following the index birth. This outcome is defined as a composite outcome. While the outcome is only specified over the longer time-period in our protocol and trial registry, exploratory analysis of this outcome during the index pregnancy will be valuable because of the strong relationship between drug use and birth outcomes. We will define the composite outcome related to substance abuse as any record in the Medicaid claims or hospital discharge data with a code listed in Table 1.1. We will also examine robustness to a definition in which we exclude the tobacco codes which we expect to make up the majority of claims we observe matching to maternal substance use.

Next, we will examine maternal experience of violence or homicide during the index pregnancy and during the first 24 months after the index birth using a combination of death records and Medicaid and hospital discharge data. This is defined as any record matching a code listed in

---

ii In our study protocol (McConnell et al 2020) we indicated that we planned to derive neonatal morbidity from discharge records. However, in order to make our analyses parallel with other analyses looking at neonatal morbidity (Han et al 2020) and because of concerns about the ability to translate these concepts directly into claims data (Ford et al 2007), we plan to rely instead on birth certificate data.

Table 1.2. As above, experience of violence was originally specified over 24 months, but we will explore analysis of this outcome during the index pregnancy because of the negative associations between exposure to maternal violence and birth outcomes. Our current definitions of substance abuse and maternal experience of violence are limited to the codes defined here; however, we will explore incorporating broader indicators of challenges with substance abuse derived from pharmacy claims, child claims, and criminal justice records. We will update these outcome specifications prior to any analysis of comparisons across treatment and control groups for these outcomes.

We will also examine use of social services during pregnancy and during the first 24 months after delivery. During pregnancy, we will examine any receipt of WIC benefits (derived from the birth certificate) and any receipt of Supplemental Nutrition Assistance Program (SNAP) benefits (from South Carolina Department of Social Services data). During the first 24 months after delivery, we will examine total months of receiving SNAP benefits and Temporary Assistance for Needy Families (TANF) benefits, as well as a measure of benefit churn, defined as receiving SNAP or TANF benefits at any time during a given year and having experienced at least one break in participation of four months or less that started and/or ended during the year.

Table 1.1. Codes for composite outcomes related to neonatal abstinence disorder and maternal drug/substance abuse

Code Description	ICD-10 Code(s)
Neonatal abstinence disorder	P96.1, P04*
Opioids	F11.*
Tobacco	F17.2*, O99.33*, Z72.0
Alcohol	V11.3*, F10.*
Sedative	F13.*
Cocaine	F14.*
Amphetamines	F15.*
Cannabis	F12.*

Source: Jarlenski et al. 2020^16

Table 1.2. Codes for maternal experience of violence

Code Description	ICD-10 Code(s)
Adult neglect	T74.01; T76.01
Adult physical abuse	T74.11; T76.11
Adult sexual abuse	T74.21; T76.21
Adult psychological abuse	T74.31; T76.31
Unspecified adult maltreatment	T74.91; T76.91

Husband, perpetrator of maltreatment	Y0701
Assault by unarmed brawl	Y040
Observation after rape	Z0441
Assault by other bodily force	Y048
Unspecified perpetrator of maltreatment	Y079
Other family member perpetrator of maltreatment	Y07499
Encounter for mental health services for victim of spousal or partner abuse	Z691x
Encounter for mental health services for victim or perpetrator of other abuse	Z698x
Encounter for observation following alleged adult physical abuse	Z0471

Sources: Crosswalk of ICD-9 to ICD-10 codes from Davidov et al. 2017 and Schafer et al. 2008.

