For inpatient mental health outcomes, we will use hospital discharge data to measure mental health related visits on both the extensive and intensive margins. Specifically, we will create an indicator for any mental health related emergency or inpatient visits during pregnancy or the 12 months postpartum based on all-listed diagnoses (i.e. primary or secondary) for depression/anxiety/stress reaction, excluding inpatient claims on the day of delivery. We will also create a count variable for the number of mental health related emergency or inpatient visits during pregnancy or the 12 months postpartum based on all-listed diagnoses for depression/anxiety/stress reaction, excluding inpatient claims on the day of delivery. We examine these hospital-related outcomes because public insurance pays for six of every ten inpatient stays related to mental health, and they could indicate inadequate outpatient treatment for perinatal depression and anxiety. We may also look at diagnoses for depression/anxiety/stress on the day of delivery, as prior research has found that a large proportion of women have diagnoses on this day. These diagnoses may represent cases where women had subclinical or previously unidentified symptoms during pregnancy that were identified during the hospital stay. Finally, we may construct an outcome that captures the proportion of women who have an emergency or inpatient stay related to mental health without any medication or outpatient psychotherapy treatment during pregnancy or the 12 months postpartum.

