### 3.2.2. Construction of contraception outcomes

Table 3.2 summarizes outcomes related to the utilization of contraceptive methods. The primary data source used for the contraception outcomes will be Medicaid claims data. Medicaid claims capture contraceptive provision among Medicaid enrollees that takes place in the hospital before discharge (inpatient), during outpatient hospital visits, and during ambulatory clinical visits. We will rely primarily on Medicaid claims data because most postpartum contraceptive provision occurs after hospital discharge. However, we will also supplement Medicaid discharge data with hospital discharge data to capture any inpatient contraceptive provision that may be missing from Medicaid claims. Any family planning related counseling or service will include any diagnosis code, procedure code, CPT code, or HCPCS codes for contraceptive counseling, the intrauterine device, implant, injectable, contraceptive pill, patch, ring or diaphragm (See Table 3.3 below) and National Drug Codes for the contraceptive pill, patch, and ring identified by the Office of Population Affairs Contraceptive Care Measures. Receipt of a moderately effective method of contraception will include all of the above methods but will not include contraceptive counseling without provision of a contraceptive method. Immediate postpartum contraception will include diagnosis, procedure, CPT or HCPCS code for an intrauterine device or contraceptive implant.

Contraceptive counseling and/or contraceptive receipt within six weeks of hospital discharge will meet the criteria for the 6-week contraceptive outcomes. Contraceptive counseling and/or receipt within 12 months of the date of hospital discharge will meet the criteria for the 12-month contraceptive outcomes.

Table 3.2. Contraceptive outcomes

Variables	Follow-up
Any family planning related counseling or service	6 weeks
Received a highly or moderately effective method of contraception 	6 weeks
Immediate postpartum long-acting reversible contraception	6 weeks
Any family planning related counseling or service	12 months
Received a highly or moderately effective method of contraception 	12 months
Postpartum intrauterine device insertion	12 months
Time to first family planning counseling or service (months from pregnancy)	24 months

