**Table 7. Postpartum outcomes**

	Primary/secondary	Desired direction (increase or decrease)
Maternal mortality (1y)	secondary	decrease
Postpartum visit (12w)	secondary	increase
Hospitalization (12w/1y)	exploratory	decrease
Outpatient visit (12w/1y)	exploratory	increase

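### The postpartum-visit outcome counts any Medicaid claim with Z39 or 59430 in the first 12 weeks, with no ambulatory or post-discharge condition, so a delivery-stay claim can score as an attended visit

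*SAP*

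**What the plan says.** SAP Addendum 1, section 1.2.1 Secondary Outcomes, introduces the outcome and its source: "We will examine receipt of any postpartum visit within the first 12 weeks postpartum using Medicaid claims data". The operational rule follows in the same sentence: "defined as a claim with a diagnosis code of Z39 or a HCPCS code of 59430". That is the whole definition. It has an upper limit of 12 weeks, two code routes and one data source. It gives no place of service, claim type, start day or link to the delivery discharge date.

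Two other places in the SAP bear on it:

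- Addendum 3, section 3.2.2, describes what the Medicaid file holds. The claims cover provision that "takes place in the hospital before discharge (inpatient), during outpatient hospital visits, and during ambulatory clinical visits". Inpatient claims from before discharge are therefore in the source data.
- Addendum 1, Maternal utilization of mental health services, builds its emergency and inpatient visit outcomes "excluding inpatient claims on the day of delivery", and cites prior research that many women receive such diagnoses on that day.

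Addendum 4, Table 7, lists the postpartum visit at 12 weeks by label only, with an increase as the desired direction, and adds no condition.

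**The concern.** The outcome is meant to show whether a woman had a postpartum visit. As written, it shows whether one of two codes appears on any Medicaid claim between birth and week 12. These differ when a qualifying code sits on a claim from the delivery admission: a woman who never returned for care would then be scored as having attended.

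Two consequences are possible. If this happens equally often in both arms, the visit rate is inflated in each and the measured NFP effect is diluted. If it happens more often in one arm, a difference can appear with no difference in attendance.

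The documents give one reason to check for the second. Protocol section 2.1 says a Medicaid waiver helps cover the cost of NFP home visits, and SAP section B.3 describes a visit about every two weeks, or about 12 / 2 = 6 visits in the 12-week window. If any of those visits generate a Medicaid claim with a qualifying code, the intervention itself would satisfy the outcome in the NFP arm. The documents do not say how the visits are billed or coded, so this is a possibility to rule out, not a finding.

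**Working it through.** **Text check.** The plan gives no rate, effect size or power for this outcome, so there is no figure to reproduce. The two visit rules compare as follows.

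| Condition | Postpartum visit (Addendum 1, 1.2.1) | Mental-health emergency or inpatient visit (Addendum 1) |
|---|---|---|
| Care setting | not stated | emergency or inpatient |
| End of window | 12 weeks postpartum | 12 months postpartum |
| Delivery-day inpatient claims | not excluded | excluded |

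No other section supplies the missing conditions. Read literally, the postpartum-visit rule accepts a qualifying claim dated during the delivery stay.

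**Size under equal misscoring.** Let p be the true attendance rate in an arm and q the share of true non-attenders with a qualifying claim that is not a visit. Assume every true visit is captured. Then:

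- measured rate = p + (1 − p)q
- measured difference = (pT − pC)(1 − q)

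Assumptions: pC = 60%, pT = 65%, and q from 0 to 50%. None is in the documents. For power I take 3,295 NFP and 1,637 usual-care mothers with an index birth (SAP Addendum 4, Table 3) and a two-sided 0.05 test (Protocol section 5.1). Power = Φ[(d − 1.96·se0) / se1], with se0 the pooled and se1 the unpooled standard error. At q = 0, se0 = 0.01457 and se1 = 0.01469, so power = Φ[(0.05 − 0.02856) / 0.01469] = Φ(1.46) = 0.93.

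| q | Usual care | NFP | Difference (points) | Power |
|---|---|---|---|---|
| 0 | 60.0% | 65.0% | 5.0 | 0.93 |
| 10% | 64.0% | 68.5% | 4.5 | 0.88 |
| 25% | 70.0% | 73.75% | 3.75 | 0.79 |
| 30% | 72.0% | 75.5% | 3.5 | 0.75 |
| 50% | 80.0% | 82.5% | 2.5 | 0.57 |

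The difference column depends only on the 5-point effect and q. With 50% or 70% attendance in usual care and the same effect, power at q = 25% is 0.74 or 0.87, against 0.91 or 0.96 at q = 0. Mothers without Medicaid claims cannot contribute to this outcome, so the denominators are upper limits and actual power would be lower in every row.

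**Size under unequal misscoring.** With no true effect and 60% attendance in both arms, spurious difference = 0.40 × (qT − qC):

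- qC = 10%, qT = 13%: 0.40 × 0.03 = 1.2 points
- qC = 10%, qT = 15%: 0.40 × 0.05 = 2.0 points
- qC = 20%, qT = 30%: 0.40 × 0.10 = 4.0 points

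**The case against.** The strongest reply is that a missing filter does harm only if the qualifying codes really appear on claims that are not visits, and the documents do not show this. They do not define Z39, and the account of inpatient claims in Addendum 3 concerns contraception. That reply stands as to size: q may be small. It does not remove the defect. The rule is stated as complete, the file contains delivery-stay claims, and nothing stops one from qualifying.

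The mental-health exclusion can also be called specific to its outcome. An inpatient stay is itself the event there, and only the delivery day is excluded. This is fair, and the comparison supports no more than that the authors saw the delivery admission as a source of false visits in claims data.

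A reader might infer several stronger points that the documents do not support:

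- That the contraception outcomes already apply the guard missing here, because they run "Contraceptive counseling and/or contraceptive receipt within six weeks of hospital discharge". They do not. Section 3.2.2 deliberately counts inpatient provision before discharge; discharge sets the end of the window.
- That Z39 as a family takes in immediate post-delivery or lactation care, so only one sub-code should count. That rests on coding knowledge outside the documents. The outcome is also any postpartum visit, so dropping lactation-only claims would be a preference.
- That the Addendum 4 postpartum index inherits the problem. The link is a label in Table 7. Addendum 4 takes its outcomes from manuscripts, and some definitions there have moved: family planning service is at 12 weeks in Table 6 against 6 weeks in Addendum 3, and lead screening at 15 months in Table 9 against 24 months in Addendum 2.

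The cited protocol paper, which was not available, may hold more detail. The SAP introduction, however, says that this plan is where outcome definitions are given in detail.

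**Conclusion.** The concern holds for one secondary outcome. The rule lacks an ambulatory-setting condition and a post-discharge condition, and followed literally it can score a delivery-stay claim as an attended visit.

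How often this happens is unknown. Equal misscoring biases the difference toward zero by the factor (1 − q): under the assumed 60% and 65%, 5.0 points becomes 4.5 at q = 10% and 3.5 at q = 30%. Unequal misscoring could produce a spurious difference of a point or more, in favour of whichever arm has the higher q. The attenuation formula assumes that true visits are always captured.

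It would be wrong to conclude that misscoring has been observed, that it favours NFP, or that any primary outcome is affected. The documents give no q in either arm, and the primary outcomes do not use this rule.

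**What to change.** Amend the definition in Addendum 1, section 1.2.1 Secondary Outcomes, so that the outcome is met by an outpatient or ambulatory Medicaid claim with 59430 or Z39, dated after discharge from the delivery admission and through 12 weeks postpartum. In addition:

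- State whether claims for NFP home visits count. An outpatient filter alone may not remove them.
- Tabulate qualifying claims by setting, date relative to delivery discharge, and arm. This shows directly how many women qualify only through a delivery-stay claim.
- Keep the present any-claim rule as a sensitivity analysis.
- If results under the present rule have already been reported, label the tightened version as added afterwards and show both.

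Restricting Z39 to a sub-code, or excluding lactation-only claims, is optional.

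The cost is a sentence or two of SAP text, a filter on claim setting and service date, and one table. The delivery discharge date is already needed for the contraception outcomes in Addendum 3. The reported visit rate may be slightly lower.

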Depression	F53; O906; F99; O9934*; F32*; F33*
Anxiety	F41.*
Stress-reaction	F43.*

Table 1.5. Therapeutic class codes for filled antidepressants or anxiolytics

Code description	Therapeutic class codes
Antidepressants	281604

Anxiolytics	2824*
-------------	-------

Table 1.6. Outpatient psychotherapy codes

Code description	CPT codes
Psychotherapy (individual, family or group)	90804-90815; 90832-90834; 90836- 90840; 90845-90847; 90849; 90853; 90857; 90862; 90875; 90876

We will also look at these outpatient measures individually (i.e., diagnosis, filled prescription, and psychotherapy) and in combination to enhance our understanding of treatment patterns. For example, we may be interested in the proportion of mothers who receive a diagnosis but do not fill a prescription or receive psychotherapy as this could signal structural or individual-level barriers to treatment. We may also be interested in the proportion of women who receive medication only, as psychotherapy is often recommended as a first-line treatment for mild or moderate depression and in combination with medication when the depression is severe. We may also explore the timing of outpatient mental services (measured in days). NFP could lead to earlier treatment of perinatal depression/anxiety through regular screening, coordinating care, providing a warm hand-off, or by reducing the stigma surrounding mental health and treatment.

For most of the outcomes related to outpatient mental health treatment, we restrict the measurement period to pregnancy through 60 days postpartum because these outcomes are derived from Medicaid claims data and maintenance of coverage past 60 days may be affected by participation in NFP. However, depression and anxiety can take longer than 60 days to manifest, and even longer for the mother to access healthcare. In future analyses, we will consider measuring outpatient mental health treatment patterns through 6, 12 and 24 months postpartum if treatment and control group members are equally likely to be enrolled in *full-coverage* Medicaid plans through these time points.

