### **1.3. Timing of Study analyses**

We will wait to complete this analysis until all study births have taken place and have completed administrative records which have been sent to the study team and matched to

existing analytic files. We will first publish our analysis of the primary outcome (described above) together with secondary outcomes related to maternal and infant health that can shed light on understanding impact estimates for the primary outcome. Following the publication of those results, we plan to produce separate analyses exploring the impact of NFP on maternal and infant outcomes related to the period of childbirth and the postpartum period, antenatal care and mental health care utilization. At 24 months, we plan to examine women's substance abuse, experience of violence, and use of social services, as described above. We may also examine mechanisms of these outcomes, for example, via nurse referrals. If Medicaid coverage is not differential between treatment and control group mothers at 24 months postpartum and the groups remain comparable, we may also explore outpatient mental health treatment patterns for up to two years after birth since the trajectory of depression symptoms in the postpartum period is increasingly understood to vary widely.

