### **2.5. Endogeneity of Data Sources and Sensitivity Analysis**

As discussed above, because child preventative health outcomes will be observed exclusively in Medicaid claims data, we will not observe these outcomes among children who are not enrolled in Medicaid. Because NFP may affect maintenance of Medicaid coverage through the child's first two years of life, child enrollment rates in Medicaid may differ between control and treatment groups.

We will conduct several analyses to determine whether rates of enrollment in Medicaid differ between treated and control groups. First, we will compare enrollment through the first year of life and the first two years of life across treatment and control groups. Even if we do not observe differences in Medicaid enrollment rates between the two groups, the type of children retaining coverage may be influenced by participation in NFP. Therefore, we will also test

whether there are differences in the characteristics of participants between control and treatment groups over the two time periods (12 months and 24 months). We will use a joint F-test to compare characteristics measured at baseline across these two groups using the list of baseline covariates specified in section B.1.

When conducting study analyses, we will report outcomes observed over the first year of life, where more children are likely to be enrolled in Medicaid as well as outcomes over the first 24 months of life. As specified in our study protocol in Section 2.12, we will report our primary outcome excluding data that comes from Medicaid to assess the robustness of our results to this potential source of endogeneity. If we observe significant differences in Medicaid enrollment across treatment and control groups in the second year of life, we may focus more on outcomes that can be measured within the first year of life.

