**Table 8. Mental health outcomes**

	Primary/secondary	Desired direction (increase or decrease)

Any outpatient treatment or diagnosis (preg-60d)	secondary	increase
Antidepressant prescription (preg-60d)	secondary	increase
Outpatient mental health visit (preg-60d)	secondary	increase
Treatment follow up (within 120d)	secondary	increase
Mental health related emergency/inpatient visit (preg-1y)	secondary	decrease
Number of mental health related emergency/inpatient visits (preg-1y)	secondary	decrease
Neonatal abstinence disorder or maternal drug/substance use (2y)	secondary	decrease
Maternal experience of violence or homicide (2y)	secondary	decrease

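### The 24-month maternal substance-abuse and violence outcomes depend partly on Medicaid claims, but no Medicaid-free re-analysis or interpretation rule is tied to them if coverage differs by arm

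*SAP*

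**What the plan says.** **The two outcomes (SAP Addendum 1, Secondary Outcomes).** The plan specifies "the composite outcome related to substance abuse as any record in the Medicaid claims or hospital discharge data with a code listed", the codes being those of Table 1.1. It covers the index pregnancy alone and also runs "over the period spanning the index pregnancy and the first 24 months following the index birth". Violence or homicide is examined in the index pregnancy as well as "during the first 24 months after the index birth using a combination of death records and Medicaid and hospital discharge data". Section 1.1 sets the sample for outcomes other than the adverse birth outcome as mothers with an index birth, with no coverage condition. The one robustness check named for substance abuse drops the tobacco codes.

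**Coverage.** Discharge data are all-payer (mental health section of Addendum 1). Section 3.5 says women with pregnancy Medicaid, apart from some immigrants, keep it for at least 60 days after childbirth, and that NFP may affect coverage after that. Table 2 gives income limits for 2016-2020 of 199% of poverty for pregnant women and 67% for parents.

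**How other outcomes are handled.**
- Most outpatient mental health outcomes stop at 60 days because "these outcomes are derived from Medicaid claims data and maintenance of coverage past 60 days may be affected by participation in NFP". Section 1.3 allows an extension to two years only under a condition: "If Medicaid coverage is not differential between treatment and control group mothers at 24 months postpartum and the groups remain comparable".
- For the child primary outcome, section 2.5 says "we will report our primary outcome excluding data that comes from Medicaid to assess the robustness of our results".
- For contraception, section 3.5 moves emphasis to 6 weeks if NFP is found to have affected enrolment.

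In the same paragraph as the mental-health condition, section 1.3 plans a 24-month analysis of women's "substance abuse, experience of violence, and use of social services, as described above", with no condition.

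**The concern.** Under an any-record rule, a woman with no visible record is scored as event-free. After 60 days, a woman who has left Medicaid can still be picked up by an all-payer hospital record or a death record, but not by an outpatient claim. If the arms keep Medicaid at different rates, they are watched with different intensity.

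Addendum 4, Table 8 gives both outcomes a desired direction of decrease. If NFP helps women stay on Medicaid, its arm accumulates more recorded harm at the same true rate, which could hide a real reduction or show an apparent increase. If retention falls, the bias mimics a benefit. Both outcomes also feed the Addendum 4 mental-health index.

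**Working it through.** **Nothing to reproduce.** The documents give no event rate, coverage rate or power for these outcomes. What follows is illustration.

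**Inputs from the documents.** Mothers with an index birth: 3,295 NFP and 1,637 control (Addendum 4, Table 3). Two-sided 5% test (protocol 5.1). Guaranteed coverage of about 2 months after birth (section 3.5).

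**Assumed inputs.** Pregnancy of 9 months; true rate p; share s of events visible only in Medicaid claims; control coverage after 60 days c = 40%; coverage gain d under NFP; no true effect.

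**Share of the window outside guaranteed coverage.** Substance abuse: (33 - 11)/33 = 67%. Violence, counting only the months after birth: (24 - 2)/24 = 92%.

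**Model 1: events at a constant rate over T = 33 months, with G = 11 months covered for all.**
- lambda = -ln(1 - p)/T
- Recorded rate if covered = p
- Recorded rate if uncovered, U = 1 - exp(-lambda x [G + (T - G)(1 - s)])
- Recorded rate in an arm = coverage x p + (1 - coverage) x U
- Spurious difference = d x (p - U)

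Worked case, p = 30%, s = 50%, d = 10 points:
- lambda = -ln(0.70)/33 = 0.01081
- U = 1 - exp(-0.01081 x 22) = 0.2116
- Control: 0.40 x 0.30 + 0.60 x 0.2116 = 0.2470
- NFP: 0.50 x 0.30 + 0.50 x 0.2116 = 0.2558
- Difference 0.0088; SE = sqrt(0.2558 x 0.7442/3295 + 0.2470 x 0.7530/1637) = 0.0131; z = 0.675
- Chance of a significant result = [1 - Phi(1.96 - 0.675)] + Phi(-1.96 - 0.675) = 0.099 + 0.004 = 10%

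| p | s | d | Spurious difference | False-positive rate |
|---|---|---|---|---|
| 10% | 25% | 10 points | +0.16 points | 5.4% |
| 10% | 75% | 20 points | +0.97 points | 23% |
| 30% | 50% | 10 points | +0.88 points | 10% |
| 30% | 50% | 20 points | +1.77 points | 27% |
| 30% | 75% | 10 points | +1.37 points | 19% |
| 30% | 75% | 20 points | +2.73 points | 58% |

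Reversing the sign of d reverses the difference: at p = 30%, s = 50%, d = -10 points, NFP records 0.40 x 0.30 - 0.10 x 0.30 + 0.70 x 0.2116 = 23.8% against 24.7%.

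**Early first records.** Suppose a share e of positive women are first recorded by 60 days. Then U = p x [e + (1 - e)(1 - s)]. With p = 30%, s = 50%, d = 10 points:
- e = 60%: U = 0.24, difference 0.10 x (0.30 - 0.24) = +0.6 points, false-positive rate 7.3%
- e = 80%: U = 0.27, difference +0.3 points, false-positive rate 5.6%

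**Model 2: a different parameterisation.** Let a be the share recorded whatever the later coverage, and q the added chance of a Medicaid-only record after 60 days if covered. Spurious difference = (1 - a) x q x d.
- Violence, a = 3%, d = 10 points: q = 2% gives 0.97 x 0.02 x 0.10 = +0.19 points; q = 5% gives +0.48 points. The chance of a significant result against NFP is 5.0% or 10.4%, against a nominal 2.5%.
- Masking, substance abuse, a = 20%, q = 10%, true 10% relative reduction in both components. Control: 0.20 + 0.80 x 0.10 x 0.40 = 23.2%. NFP: 0.18 + 0.82 x 0.09 x coverage, giving 20.95%, 21.7% and 22.4% at coverage of 40%, 50% and 60%. Power to show the benefit is 44%, 23% and 9%.

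With equal coverage, d = 0 and the bias is zero in both models.

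**The case against.** **What stands.**
- The gap is not hidden. The mental health section compares full-coverage enrolment by arm to 24 months, with a joint F-test on baseline characteristics, and section 3.5 does the same for other coverage types. A reader might infer that a coverage effect and a true effect could not be told apart. That goes too far: a difference in coverage would be seen. What is missing is any consequence for these two outcomes.
- The index-pregnancy versions fall largely within pregnancy coverage. They are exploratory, and are justified by the link with birth outcomes rather than by coverage.
- A reader might infer that every other claims outcome is protected. It is not: the 12-week postpartum visit comes from Medicaid claims, runs past 60 days and has no stated safeguard, and the main contraception analysis keeps all women whatever their later coverage.
- Uniform event timing probably overstates the bias for substance abuse. The composite includes newborn and pregnancy codes, tobacco is expected to dominate, and one record is enough.
- Homicide appears in death records, and inpatient and emergency records are all-payer. Only later outpatient claims are exposed.

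**What does not remove the point.** The Secondary Outcomes section promises updated specifications before arms are compared, but for broader indicators, not coverage; pharmacy claims, if from Medicaid, would add coverage dependence. Section A.2 promises to describe missing data where possible, in general terms, and leaves details to the addenda. The published protocol paper is not among the documents, but the SAP cites its Medicaid exclusion only for the child primary outcome.

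**Conclusion.** The point holds for the 24-month versions of both outcomes. Their definition makes ascertainment depend on maternal Medicaid coverage after about 60 days, the SAP says NFP may affect that coverage, and neither a Medicaid-free version nor an interpretation rule is attached, although both devices are used elsewhere in the SAP.

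The size is unknown. Under the assumed inputs it runs from negligible (about 0.2 points, false-positive rate about 5%) to 1-2 points or more (10-27% or higher) when the coverage gap and the Medicaid-only share are both large. The 58% figure needs a 20-point gain and a 75% Medicaid-only share together, and no document supports either. If most women are first recorded by 60 days, the 10-point case falls to 0.3-0.6 points.

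A reader might also infer that NFP will look worse. The documents do not support that: the direction depends on whether retention rises or falls, and nothing here says which. These are secondary outcomes, so this is a change worth making rather than a threat to the trial's main conclusions.

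**What to change.** In SAP Addendum 1, Secondary Outcomes and section 1.3:

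1. Report each 24-month outcome also from all-payer discharge and death records only, beside the all-source version, following section 2.5.
2. Report the all-source version for pregnancy through 60 days postpartum.
3. Extend the existing coverage condition in section 1.3 to these two outcomes: if the coverage comparison already planned in the mental health section is differential, emphasis moves to versions 1 and 2.
4. In Addendum 4, rerun the mental-health index with version 1 as a sensitivity analysis. Two of the eight items in Table 8 are affected.

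**Cost.** SAP wording and a few table rows, with no new data. Version 1 removes the dependence on coverage but has fewer events and less precision. It may also respond to NFP through emergency department use, which Addendum 4 says could go either way. The all-source version should therefore be kept alongside it.
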